16.3 Methods for Randomization and Stratification

This study is a non-randomized, single arm study of female patients with invasive ductal carcinoma receiving accelerated chest wall irradiation following mastectomy. Thus, there is no randomization or stratification.

16.4 Outcome Measures

Time to local, regional, and/or distant failure will be recorded for primary endpoint analysis. Secondary endpoints will be measured by the data collected for toxicity as dichotomous variables; need for cosmetic reconstruction revision will also be collected and analyzed as a dichotomous variable.

16.5 Statistical Analysis

All time intervals will be calculated from the date of diagnosis. Fisher's exact test will be performed to correlate clinicopathological covariates with toxicity and with plastic surgical revision. The association of variables with LR failure times will be investigated by fitting a parametric model and examining the significance of the parameter estimates. Nonparametric estimates of the survival or recurrence-free distributions or recurrence (failure) distribution will be obtained by life table methods. Tests will be declared statistically significant if the calculated P-value was ≤ 0.05 . All tests appear as 2-sided P-values.

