4.1 Duration of Study

Patients will be enrolled in this trial over the course of approximately 36 months. The duration of the protocol for each patient will be from the date of registration to the last day of radiation therapy. Patients will be followed regularly after treatment as per standard departmental policy (Section 9.2.1). The duration of the study is estimated to be 72 months, such that the minimum follow-up in the study cohort is 36 months.

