4.2 Study Design

[figure not shown]
This study is a non-randomized, single arm study of female patients with early stage or advanced invasive ductal, lobular, medullary, papillary, colloidal (mucinous), or tubular carcinoma receiving accelerated chest wall irradiation following mastectomy.

A patient who is diagnosed with breast cancer will be seen by their surgeon for evaluation of their cancer, discussion of surgical management, and possible enrollment onto clinical trials, including this trial.

- The patient has 14-63 days from the date of last surgery or date of last chemotherapy cycle to register and undergo CT simulation. Then the patient has 21-63 days after the last surgery/last chemotherapy cycle to start radiation therapy.
- PMRT may be delivered before cytotoxic chemotherapy.
- If chemotherapy is delivered after radiation therapy, it must begin no earlier than 21 days following completion of radiation therapy.
- All patients will meet with a medical oncologist or medical oncology nurse prior to beginning RT.
- All patients will receive radiotherapy based on CT treatment planning.
- If the patient underwent a mastectomy at an outside facility, she will still be eligible for the trial if all other eligibility criteria are met.
- Hormonal therapy, if indicated, can be initiated before, during or after radiation at the discretion of the treating physicians.

[REDACTED]

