5.1 Inclusion Criteria

- 5.1.1 Invasive ductal, medullary, papillary, colloid (mucinous), or tubular histologies. Invasive lobular carcinomas are allowed.
- 5.1.2 AJCC Stage IIa – IIIc (pathologic stage T0N1-3, T1N1-3, T2N1-3, T3N0-3, T4N0-3, all M0 status) histologically confirmed invasive carcinoma of the breast treated with mastectomy and either sentinel node biopsy or axillary dissection. Inflammatory carcinoma (T4d) is allowed.
- 5.1.3 Patients with locally advanced breast cancer on clinical exam and diagnostics (> 3 cm and/or clinically node-positive) who have mastectomy after induction chemotherapy are allowed.
- 5.1.4 Multifocal/multicentric disease is allowed.
- 5.1.5 Negative inked histologic margins of mastectomy (no invasive cells at margin) or positive margin at pectoralis fascia or skin.
- 5.1.6 Tamoxifen, Arimidex or other hormonal therapy is allowed. It may begin any time relative to the radiation at the discretion of the treating physician.
- 5.1.7 Chemotherapy is allowed. If chemotherapy is indicated the chemotherapy can be delivered first, followed by radiation therapy beginning 21-63 days after the last cycle of chemotherapy or the radiation therapy can be delivered first and the chemotherapy can be delivered no earlier than 21 days post radiation therapy. Neoadjuvant chemotherapy is allowed; radiation therapy will be delivered after mastectomy or after any adjuvant chemotherapy as described above.
- 5.1.8 Chest wall reconstruction is allowed.
- 5.1.9 The patient must be enrolled and have treatment planning between 14 – 63 days from date of last surgery or last cycle of chemotherapy, and radiation must start within 21-63 days of date of last surgery or last cycle of chemotherapy.
- 5.1.10 Women must be \geq 18 years of age.
- 5.1.11 Signed study-specific informed consent form prior to study entry.
- 5.1.12 ECOG performance status of 0 or 1.

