Appendix D

Case Report Forms

CASE REPORT FORM #1 – PATIENT ENROLLMENT

Patient Identification:		  -    	Site	Sequential						
1. Enrollment Date:		  /   /  	M M	D D	Y Y	2. Date of Birth:	  /   /  	M M	D D	Y Y
3. Age at Diagnosis:		 	4. Menopausal Status:		 Pre	 Peri	 Post			
5. Race:		 Black	 Caucasian	 Hispanic	 Asian	 Other				
6. Histology:										
 Invasive ductal		 Pure DCIS		 Invasive lobular		 Other				
7. Grade:		 I	 II	 III						
8. AJC Classification:		Tis:		 T1	 T2					
		If T2, ≤ 3 cm		 Yes	 No					
9. Largest Tumor size:		  mm								
10. Surgical Margins:										
 Negative (no tumor on ink)		 Close (< 2 mm)		 ≥ 2 mm						
11. Nodes:		Negative	 Yes	 No	Numbered Excised:		Number positive:			
12. Sentinel node biopsied:		 Yes	 No	Axillary Dissection:		 Yes	 No			
13. Estrogen receptors – Positive: Value = _____				 Yes	 No	 Unknown				
14. Progesterone receptors – Positive: Value = _____				 Yes	 No	 Unknown				
15. Her2Neu – Positive:				 Yes	 No	 Unknown				
16. Adjuvant therapy for this cancer episode:										

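### Failure times start at diagnosis although patients enter only after mastectomy and sometimes chemotherapy, so the life-table and parametric analyses credit sequence-dependent pre-entry time; the bias is small and touches no decision rule

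*Combined protocol and SAP*

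**What the plan says.** Section 16.5 fixes one origin for everything: "All time intervals will be calculated from the date of diagnosis". It then plans life-table estimates of the recurrence and survival distributions and a parametric model relating covariates to locoregional failure times. It mentions no delayed entry, left truncation or landmark, and no other section sets a different origin.

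Entry comes later than diagnosis. Criterion 5.1.2 requires disease already "treated with mastectomy and either sentinel node biopsy or axillary dissection". Under 5.1.9, registration and planning fall 14 to 63 days after the final operation or chemotherapy cycle. For treatment itself the criterion states: "radiation must start within 21-63 days of date of last surgery or last cycle of chemotherapy". Chemotherapy can come at several points. On treatment before radiation, 5.1.7 says: "Neoadjuvant chemotherapy is allowed; radiation therapy will be delivered after mastectomy or after any adjuvant chemotherapy as described above". Section 4.2 also allows the reverse order: "PMRT may be delivered before cytotoxic chemotherapy".

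Section 4.1 gives the follow-up: "The duration of the study is estimated to be 72 months, such that the minimum follow-up in the study cohort is 36 months". CRF #1 in Appendix D, as printed, has the enrolment date and the mastectomy date, but for diagnosis only the item "3. Age at Diagnosis".

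**The concern.** A patient is not under observation in this trial between diagnosis and registration. A woman whose disease spreads in that period is excluded as M1. One who recurs locally before radiation would not ordinarily be entered into a study of adjuvant chest wall irradiation. Counting that period as time at risk is left truncation that the analysis ignores (immortal time).

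Two things follow. First, the life-table failure estimate at any fixed time is too low, always in the favourable direction. Second, the uncounted lag is short when radiation precedes chemotherapy and long when chemotherapy comes first. In the parametric model, any covariate tied to that sequence would then look protective without being so. The trial has a single arm, so no concurrent control group shares the shift and cancels it.

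**Working it through.** **The plan's own figures.** The 90% interval in 16.2 for 5 recurrences among 67 patients (3.7% to 14.5%) is reproduced by the Wilson score method: 3.68% to 14.55%. The toxicity rule (reject at 5 or more of 67, 3% against 9%) gives an exact level of 0.0508 and power of 0.732, as stated. Both are counts over a fixed number of patients. No time origin enters, so neither changes.

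**Inputs for the lag.**
- From 5.1.9: 21-63 days from last surgery or last chemotherapy cycle to radiation, which is 21/30.44 = 0.69 to 63/30.44 = 2.07 months.
- Assumed, not in the documents: 1 month from diagnosis to surgery, and 4-6 months of chemotherapy when it precedes radiation.
- From 2.2: 6% locoregional recurrence at 5 years in irradiated node-positive patients. A constant hazard is assumed: h = -ln(0.94)/60 = 0.00103 per month.

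**Lag from diagnosis to radiation.**
- No prior chemotherapy: 1 + 0.69 = 1.7 to 1 + 2.07 = 3.1 months.
- Prior chemotherapy: 1 + 4 + 0.69 = 5.7 to 1 + 6 + 2.07 = 9.1 months.

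Measured to registration (14 days at the earliest) instead of radiation, the lower ends fall by 7 days, about 0.2 months.

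**Effect on the life table.** Failure at 36 months from radiation is 1 - exp(-36h) = 3.64%. With lag L, the value read at 36 months from diagnosis is 1 - exp(-(36 - L)h):

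| Lag L (months) | Failure read at 36 months | Understatement (points) |
|---|---|---|
| 1.7 | 3.48% | 0.17 |
| 3.1 | 3.34% | 0.31 |
| 5.7 | 3.08% | 0.57 |
| 9.1 | 2.74% | 0.91 |

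A mixed cohort falls between these values according to its share of each sequence.

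**Effect on the parametric model.** Take two groups with the same true hazard and the same mean follow-up F from radiation, with lags of 8 months (chemotherapy first) and 2 months (radiation first). An exponential fit from diagnosis gives a hazard ratio of (F + 2)/(F + 8). This is 38/44 = 0.86 at F = 36 and 56/62 = 0.90 at F = 54. The second value of F is the mean if 36 months of even accrual leave 36 to 72 months of follow-up.

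A Weibull simulation of 200,000 patients supports this. It assumed no covariate effect, 7.5% failure at 5 years, lags of 1.5-3 against 6-9 months, and 36-72 months of follow-up:

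| Analysis | Hazard ratio | Weibull shape |
|---|---|---|
| From radiation | 0.985 | 1.00 |
| From diagnosis | 0.878 | 1.27 |
| From diagnosis, delayed entry | 0.983 | 1.01 |

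The departure of 0.985 from 1 is within simulation error. Either correction removes the distortion.

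**Against sampling error.** The binomial standard error of 3.64% with 67 patients is sqrt(0.0364 × 0.9636/67) = 2.3 points. Expected locoregional events are 67 × (1 - exp(-54h)) = 3.6 at 54 months and 67 × 0.0364 = 2.4 at 36 months. With an even split, the standard error of a log hazard ratio is about 2/sqrt(3.6) = 1.05 and 2/sqrt(2.4) = 1.3. The spurious log ratios are ln 0.90 = -0.10 and ln 0.86 = -0.15, about a tenth of those.

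**The case against.** The strongest reply is that nothing the trial decides depends on this. That stands. A reader might infer that the bias favours the non-inferiority conclusion. The documents do not support that: the only stated criterion is the crude count in 16.2, and no success threshold rests on a life-table estimate. This is so even though 1.1 and 16.4 tie locoregional outcome or failure times to the primary endpoint.

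The effect is also lost in the noise of 67 patients, as the standard errors show. Section 16.5 names no covariates for the model, so the chemotherapy-sequence example is conditional on such a term being fitted. If later stage goes with a longer lag, any true adverse effect of stage would be attenuated; the documents do not show that stage would end up looking protective.

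Other inferences also go too far:
- **Benchmark clocks.** Section 2.2 describes trials that randomised after mastectomy, but does not say from when their recurrence rates were counted. A mismatch of clocks is not shown.
- **Missing diagnosis date.** Section 13.1 leaves the collected data to a separate data capture plan that is not shown. The printed CRF #1 does not prove that the date goes uncollected.
- **Toxicity.** It is analysed as a dichotomous variable (16.4), so no planned toxicity result moves with the origin.
- **Guaranteed event-free time.** Section 5.2 names M1 disease but not locoregional recurrence between surgery and entry. The accurate statement is that essentially no trial event can be recorded then.

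None of this defends diagnosis as the origin. The estimator is biased in a known direction as written, and the remedy is simple.

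**Conclusion.** The point holds as a correction to the analysis text of modest weight. Counting from diagnosis without delayed entry understates 36-month locoregional failure by about 0.2-0.9 percentage points on a true 3.6%. It would give a null chemotherapy-first covariate a hazard ratio of about 0.86-0.90. The direction follows from 5.1 and 16.5 alone. The size rests on the assumed diagnosis-to-surgery and chemotherapy durations, the constant hazard and the 6% 5-year rate; longer lags or a higher rate would enlarge it. The count-based statements in 16.2 stand as they are.

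**What to change.** In 16.5, calculate all failure-time intervals from the date of registration, or from the first radiation fraction, and name one of the two. The enrolment date is already on CRF #1, so the first choice needs no new data item. If time from diagnosis is also to be reported, analyse it with delayed entry at registration, and confirm that the data capture plan collects the date of diagnosis, adding it to CRF #1 if not.

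The cost is one sentence in 16.5 and, for the optional analysis, one date field. No treatment, visit or sample size changes. The downside is that reported control at a fixed time becomes slightly less favourable.

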16.6 Compliance and Missing Data

Compliance will be defined as patients who complete the course of radiotherapy in a time frame as described above. If a patient is unable to do so, they will be removed from the study. Data will be accumulated on a daily basis for each patient. If by chance there is missing data, it will be imputed based on the population as a whole.

17. Human Subjects

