7.10 Dose Adjustments/Delays/Modifications/Removal from study

- 7.10.1 **Treatment Breaks/Interruptions:** Radiotherapy is given in continuous course. It is not anticipated that treatment breaks should be needed. If a break seems necessary or must be given due to unavoidable medical necessity (i.e., intercurrent illness), [REDACTED]
- 7.10.2 **Removal From Study:** [name] should be notified within 48 hours by telephone or e-mail and within 7 working days by writing of the removal of a patient from protocol.
- 7.10.3 **Inability to Adequately Perform Treatment Planning:** If the radiation oncologist is unable to devise a dosimetrically-satisfactory treatment plan, then the patient will be removed from study.
- 7.10.4 **Recurrence During Treatment:** Any evidence of local, regional or distant recurrence during the period of therapy will result in removal from study. Further, local-regional and systemic therapy will be at the discretion of the attending physicians. Patients who develop recurrence subsequent to the completion of the treatment program will be managed as deemed appropriate by the attending physicians.
- 7.10.5 **Undue Toxicity:** Treatment may terminate prior to its planned completion should the attending physicians feel that the patient is suffering undue toxicity. Such situations should be discussed with [REDACTED] from study.

7.10.6 **Patient Refusal to Continue Treatment:** A patient may withdraw her consent to participate at any time. In this case, alternative therapy, or no further therapy, may be given at the discretion of the attending physician.

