8.4 Definition of Unexpected Adverse Events

8.4.1 Any adverse drug experience and/or specificity, that is not included in the current investigator's brochure and/or package insert.

9. Treatment Evaluation/Criteria for Response

- ◊ Loco-regional (LR) control will be assessed by physical examination and other relevant imaging per the discretion of the patients treating physicians. All LR failures have to be confirmed by biopsy, and should be coded as either chest wall recurrence, axilla, supraclavicular, or internal mammary.

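### Section 16.6 removes patients who do not finish radiotherapy on time and imputes missing data from the whole population, and no visible text says that late toxicity and recurrence in removed patients are counted

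*Combined protocol and SAP*

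**What the plan says.** Section 16.6 defines compliance as completing radiotherapy in a time frame given earlier in the protocol. For patients who do not, the rule is: "If a patient is unable to do so, they will be removed from the study". It then adds: "If by chance there is missing data, it will be imputed based on the population as a whole". No variables and no imputation method are named.

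Other sections bear on the same patients:

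- **Section 8** makes every patient who receives one dose evaluable for toxicity. It grades radiation-related events of grade 2 or higher during therapy and up to 30 days after the last dose.
- **Section 7.6** gives 15-19 elapsed days and typically adds 1-2 missed days to the end of the course. Longer gaps go to a consensus decision to retain or remove the patient.
- **Section 7.10.4**: "Any evidence of local, regional or distant recurrence during the period of therapy will result in removal from study". Section 7.10.5 allows early termination for undue toxicity. Section 7.10.6: "A patient may withdraw her consent to participate at any time".
- **Section 4.1**: "The duration of the protocol for each patient will be from the date of registration to the last day of radiation therapy", and then "Patients will be followed regularly after treatment as per standard departmental policy".
- **Section 10** lists off-study criteria, including noncompliance, as reasons for which treatment ends.
- **Section 9** on recurrence: "All LR failures have to be confirmed by biopsy, and should be coded as either" one of the listed sites. Section 9.1.2 has brachial plexopathy and pain recorded at each follow-up visit.
- **Section 16.4**: "Time to local, regional, and/or distant failure will be recorded for primary endpoint analysis". Section 16.5 plans life-table estimates and gives no censoring rule for removed patients.

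**The concern.** Two rules in 16.6 can change who is counted.

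The first is removal. Automatic removal from the study does not fit with Section 8's evaluability rule or with 7.6's case-by-case decision for longer gaps. If removal also ends follow-up, two kinds of event could be lost. One is late toxicity that first appears after the 30-day window, such as brachial plexopathy, which belongs to the toxicity definition in 16.2. The other is recurrence in removed patients, including the recurrence during therapy that itself causes removal. Because 7.10.4 and 7.10.5 tie removal or early termination to recurrence and toxicity, the loss can be related to outcome.

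The second is imputation. If it is applied to endpoint status, a patient whose data are missing because of toxicity or recurrence is given the average risk of the cohort.

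At stake is a decision that turns on very few events: 5 toxicity events in 67, and an interval for recurrence illustrated at up to 5 in 67.

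**Working it through.** **Inputs from Section 16.2:** n = 67; reject 3% at 5 or more events; unacceptable rate 9%; stated exact level 0.0508 and power 0.732; stated 90% interval for 5/67 recurrences 3.7%-14.5%. The documents give no removal or dropout rate, so the numbers of unobserved patients below are assumptions.

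**1. The plan's figures.** With P(X ≥ k) = Σ C(n,j) p^j (1−p)^(n−j) over j = k to n:

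- n = 67, p = 0.03, k = 5: 0.0508 (matches).
- n = 67, p = 0.09, k = 5: 0.7316 (matches 0.732).
- The Wilson 90% interval for 5/67 is 3.68%-14.55% (matches).

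**2. One event more or less.** Section 8 keeps a removed patient in the toxicity denominator, so an uncounted late event turns 5/67 into 4/67. The tail probability at 3% moves from 0.0508 to 0.1419, and the rejection is lost. For recurrence, 6/67 has a Wilson 90% interval of 4.7%-16.4%. This is the plan's illustration of acceptability, not a formal test.

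**3. Unobserved patients, true rate 9%, limit fixed at 5.**

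| Assumption | Formula | Chance of reaching 5 counted events |
|---|---|---|
| All 67 observed | P(X ≥ 5), n = 67 | 73.2% |
| 1 unobserved, unrelated to outcome | P(X ≥ 5), n = 66 | 71.9% |
| 3 unobserved, unrelated to outcome | P(X ≥ 5), n = 64 | 69.4% |
| 5 unobserved, unrelated to outcome | P(X ≥ 5), n = 62 | 66.6% |
| One true event goes uncounted (six needed) | P(X ≥ 6), n = 67 | 56.7% |

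**4. Imputation (assumed: 4 events in 64 observed, 3 missing).** Each missing patient is given 4/64 = 6.25%. Expected imputed events: 3 × 0.0625 = 0.19. Chance of at least one, and so of a fifth event: 1 − (1 − 0.0625)^3 = 17.6%. If the three truly carry a 9% risk, the chance is 1 − 0.91^3 = 24.6%. If their true risk is 6.25%, there is no difference. If they are in fact event-free, the 17.6% is the chance of a false fifth event.

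**5. The time frame.** Section 7.5 allows a start on any weekday, no weekend treatment, 11 fractions and an optional boost of up to 4. Elapsed days, counting first and last, with no missed days:

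| Fractions | Mon | Tue | Wed | Thu | Fri |
|---|---|---|---|---|---|
| 11 | 15 | 15 | 15 | 15 | 15 |
| 12 | 16 | 16 | 16 | 16 | 18 |
| 13 | 17 | 17 | 17 | 19 | 19 |
| 14 | 18 | 18 | 20 | 20 | 20 |
| 15 | 19 | 21 | 21 | 21 | 21 |

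Sections 7.6 and 17.4 give 15-19 days. Fourteen fractions from a Wednesday to Friday start, and fifteen from a Tuesday to Friday start, exceed this without any missed day. The 11-fraction course always takes 15 days, and at most 19 with two weekdays made up.

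**The case against.** The strongest reply is that removal means only the end of protocol treatment. Section 4.1 ends each patient's protocol on the last day of radiotherapy, with follow-up afterwards, and Section 10 introduces its list as reasons for which treatment stops. On that reading Section 8 still applies to every treated patient and there is no conflict with it. Section 9 covers all locoregional failures without excepting removed patients, and 16.4 records failure times. Text at the end of 7.6, in 7.10.1 and 7.10.5, and all of Section 14 is redacted, and the data capture plan is not in view. All of this stands, and it limits the point to the literal, visible text. It does not close the gap, because neither 4.1 nor Section 10 names removed patients and no visible passage says that their later events count.

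The reply also fairly notes that basing the decision on the observed count has a fault of its own. It treats missing patients as non-events, 0 expected events against 0.19 under imputation in the example. That is why the fix pairs the observed count with a missing = event analysis.

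Several stronger readings are tempting but unsupported:

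- A reader might infer that any bias must favour the regimen. Dropping event-free patients raises a proportion (5/67 = 7.5%, 5/62 = 8.1%), and imputing for them can add a false event.
- A reader might take the fall from 73.2% to 66.6% as the worst case. It assumes missingness unrelated to outcome; one lost event alone gives 56.7%.
- A reader might see a conflict in the 1-2 made-up days in 7.6. They can be read as part of 16.6's time frame. The consensus sentence that follows in 7.6 might be read in the same way, but removal in 16.6 is stated without that discretion.
- A reader might conclude that adherent patients given the full boost will be removed. The documents show only that they could meet the literal rule.

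**Conclusion.** The point holds for the plan as visibly written and should be fixed; confidence is medium. Read literally, 16.6 conflicts with Section 8 and, for longer interruptions, with 7.6. Under the milder reading, the visible text still gives no rule that late toxicity and recurrence in removed patients are followed and counted. Toxicity to 30 days is not at risk.

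If removed patients with events are not counted, the bias favours the regimen; in other cases it can run the other way. The number affected is unknown and probably small, since removal arises within a course of about three weeks. The consequence of a single event is still large relative to the limit: rejection at 5/67 (0.051) against none at 4/67 (0.142). The power and imputation figures rest on assumed numbers of unobserved patients and show sensitivity, not an expected loss. The mismatch in elapsed days needs no assumption beyond the optional boost and the start day.

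**What to change.** In 16.6, replace the removal sentence with: *Patients who stop, prolong or do not complete radiotherapy remain in follow-up (unless they withdraw consent to follow-up) and in all analyses, whatever is decided about their protocol treatment.* Then:

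- Analyse toxicity and recurrence in all patients who receive at least one fraction.
- Count recurrences during therapy as events, and censor event-free patients at last contact in the life-table analysis.
- Do not impute endpoint events from the whole population. Report the observed toxicity count with the number incompletely followed, state that the fixed 5-event limit treats these as non-events, and give missing = event as a sensitivity analysis.
- Report compliance descriptively.
- Reconcile 16.6, 7.6, 7.10, 8 and 10 on what removal from study means, and 7.5 with the elapsed days in 7.6 and 17.4. No clinical rule is proposed here.

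The cost is mainly wording, since Sections 6 and 9.1.1 already schedule visits to 5 years. The consent text is not in view and should be checked to cover continued follow-up after removal. Observed results may look slightly less favourable.
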